2.6.3. Inclusion Criteria - Repeat-treatment

Subjects who meet **ALL** the following criteria are eligible for a repeat-treatment:

1. In the opinion of the treating investigator, the subject has returned to sufficient severity of both NLFs that would have qualified him for enrollment into the clinical investigation initially (note that the subject does not have to return to his Baseline severity to be permitted to receive a repeat treatment)
2. Subjects with NLFs with severity scores of 2 or 3 on the 5 point NLF-SRS for both NLFs as judged by the treating investigator in conjunction with the independent blinded evaluating investigator (note that it is not necessary for the treating and evaluating investigator to agree on the same rating)
3. Females of childbearing age must have a negative urine pregnancy test at the repeat-treatment visit and must agree to continue to use an adequate method of contraception for the duration of the clinical investigation
4. Healthy skin in the nasolabial area and free of diseases that could interfere in cutaneous aging evaluation and/or injection

2.6.4. Exclusion Criteria - Repeat-treatment

Subjects who meet **ANY** of the following criteria are **NOT** eligible for a repeat-treatment:

1. Occurrence of a serious adverse event or adverse event of special interest (i.e. changes in vision [loss of vision, blurriness, double vision, pain in or around the eye, blindness, blind spots, problems moving the eyes, changes in peripheral vision], skin changing color around the eyelids or around the site of injection) during or after the initial injection and/or touch-up injection
2. Subjects who experienced visual changes or other serious medical conditions during or after the initial/touch-up injection
3. Subjects who have one of the following assessments during the visual examinations:
 - Snellen acuity test worse than 20/40 (with corrective eyewear, if applicable)

This document is confidential.

- Abnormal confrontational visual field test
 - Abnormal ocular motility test
4. Subjects who became pregnant since start of the study or are planning to become pregnant during the clinical investigation
 5. Known human immune deficiency virus-positive individuals
 6. Presence of infectious, inflammatory or proliferative cancerous or pre-cancerous lesions in the area to be treated
 7. Development of recurrent herpes simplex in the treatment area since study start
 8. Development of any autoimmune or connective tissue disease since start of participation in the study, or current treatment with immunomodulating therapy
 9. Development of uncontrolled (or instable) diabetes mellitus or any other systemic disease since study start
 10. Development of a bleeding disorder since study start or use of anticoagulant, antiplatelet or thrombolytic medication from ten days pre- to three days post injection
 11. Planned dental/oral surgery or modification (bridge-work, implants) within 2 weeks prior to injection and to a minimum of four weeks post injection
 12. Any medical condition prohibiting the inclusion for repeat treatment according to the judgement of the treating investigator

2.7. Determination of Sample Size

The primary effectiveness outcome measure will be evaluated by the one-sided 95% confidence interval of the difference between paired proportions $p_A - p_B$. At this, p_A is the response rate for Princess® FILLER Lidocaine and p_B is the response rate for Juvéderm® Ultra XC. Thus, a negative value of this difference means that the response rate of Princess® FILLER Lidocaine is lower than the response rate for Juvéderm® Ultra XC. Princess® FILLER Lidocaine will be considered non-inferior to Juvéderm® Ultra XC if the lower confidence limit does not exceed the non-inferiority margin of -10%.

Further assumptions for sample size calculation:

- Response rate at Week 24 for Juvéderm® Ultra XC is 88%
- Response rate at Week 24 for Princess® FILLER Lidocaine is 87%
- Proportion of subjects with response only in one NLF: 21.9% ($88.0\% * 13.0\% + 87.0\% * 12.0\% = 21.9\%$)
- Proportion of subjects with response in both NLFs: 76.5% ($88.0\% * 87.0\% = 76.5\%$)

The latter two proportions were calculated on the basis of the response rates for Princess® FILLER Lidocaine and Juvéderm® Ultra XC assuming that the two NLFs of one subject are independent. Since there should be a concordant correlation between the two nasolabial folds of one subject, this assumption is considered to be conservative.

Based on these assumptions, 222 subjects will be necessary in order to achieve a power of 90%.

Sample size calculation was done using nQuery Advisor® 7.0. The result is based on 1600 simulations using the Newcombe-Wilson score method to construct the confidence interval.

2.8. Treatment Assignment and Blinding

Randomization will be performed at Baseline (Visit 2) per clinical investigation site via interactive web response system (IWRS). Each participant will receive Princess® FILLER Lidocaine in one NLF and Juvéderm® Ultra XC in the contralateral NLF, with allocation of respective fillers to the sides randomized as follows:

Group A:

This document is confidential.

- Princess® FILLER Lidocaine on left NLF
- Juvéderm® Ultra XC on right NLF

Group B:

- Juvéderm® Ultra XC on left NLF
- Princess® FILLER Lidocaine on right NLF

The treating investigator performing the treatment will be aware of the device injected (unblinded treating investigator).

The independent blinded evaluating investigator will not be aware of the device injected.

The subject will be blinded using a blindfold.

Moreover, an evaluation of NLFs severity by three independent blinded photographic reviewers using the 5-point NLF-SRS and based on photographs will take place at the end of the clinical investigation. Each of the three independent blinded photographic reviewers will review all photographs. These independent blinded photographic reviewers, will not be aware of the treatment allocation. They will be dislocated from the clinical investigational sites, will have no access to randomization schedule, and will not discuss any findings with the treating investigators or independent blinded evaluating investigators during the clinical investigation and until the final database lock.

The randomization assignment should not be revealed before the database has been cleaned and closed.

Emergency unblinding

There will be no special procedure for emergency unblinding because the treating investigators will be aware of the treatment allocation, and the subjects will know that they have received a hyaluronic acid dermal filler with lidocaine, which is, in both cases, sufficient level of information needed in case of emergency.

2.9. Administration of Study Medication

On Day 0 (Visit 2), the Princess® FILLER Lidocaine will be injected to one NLF and the control Juvéderm® Ultra XC to the contralateral NLF of each subject, according to the randomization scheme; the left NLF will be treated first and the right NLF thereafter.

The decision to perform touch-up treatment is in the responsibility of the treating investigator and aim to obtain optimal aesthetic result, if not already achieved with the initial treatment.

A repeat-treatment will be performed with Princess® FILLER Lidocaine on both NLFs.

2.10. Study Procedures and Flowchart

All study assessments will be performed at the visits outlined in the events schedules ([Table 1](#)).

This document is confidential.

Table 1 Schedule of Clinical Investigation Procedures and Assessments

	Screening ¹	Baseline ¹	Follow-up for initial-/touch-up treatment				Evaluation for repeat-treatment/repeat-treatment ⁴				Follow-up for repeat-treatment ⁵												
			Day 3	Touch-up	Day 3 after touch-up treatment	4 Weeks Follow-up	6 Weeks Follow-up	12 Weeks Follow-up	24 Weeks Follow-up	36 Weeks Follow-up	Day 3 after Repeat treatment	48 Weeks Follow-up ¹³	Day 3 after Repeat treatment	4 Weeks Follow up after repeat-treatment at Visit 6 or 7	12 Weeks Follow up after repeat-treatment at Visit 6 or 7								
Procedure	Visit 1	Visit 2	Phone C. 1 ¹¹	Visit 3a ²	Week 2 (± 3 days)	Visit 3b	Week 4 (± 5 days)	Visit 3c	Week 6 (± 5 days)	Week 12 (±5 days)	Visit 4	Week 24 (±5 days)	Visit 5	Visit 6	Phone C. 11	Visit 7	Phone C. 11	Day 3 after Repeat treatment	Week 48 (±5 days)	Visit 8a/8b	Week 40 OR Week 52 (± 5 days)	Week 48 (±5 days) OR Week 60(±5 days)	
Informed consent	X																						
Medical /aesthetic procedures history ^a	X																						
Demographics ^b	X																						
Fitzpatrick skin type	X																						
Body weight		X		X		X	X			X		X		X		X				X		X	
Visual examinations ^c		X		X ²		X	X ⁸							X ¹⁰		X ¹⁰				X ¹⁰		X ¹⁰	
Eligibility assessment	X													X ^{5,6}		X ^{5,6}							
Randomization		X ⁶																					
Treatment		X		X ⁷										X ⁹		X ⁹							
Urine pregnancy test ^d	X	X ⁶		X ^{5,8}										X ^{6,10}		X ^{6,10}							
NLF-SRS ^e	X									X	X	X	X	X ⁶		X ⁶				X ⁶		X ⁶	
Clinical photography ^f	X	X ⁶								X	X	X	X	X ⁶		X ⁶				X ⁶		X ⁶	
FACE-Q subject														X ⁶		X ⁶							
"Satisfaction with Outcome" ^g														X ⁶		X ⁶							
FACE-Q subject appearance		X ⁶								X	X	X	X	X ⁶		X ⁶							
"Appraisal of NLFs" ^h										X	X	X	X	X ⁶		X ⁶							
GAIS ⁱ independent blinded evaluating investigator										X	X	X	X	X ⁶		X ⁶							
GAIS ⁱ subject										X	X	X	X	X ⁶		X ⁶							
Dispense subject diary		X		X		X ⁸								X ¹⁰		X ¹⁰							
Collect subject diary ^j				X		X		X ⁸						X ¹⁰		X ¹⁰							
Evaluation of pain ^k		X												X ¹⁰		X ¹⁰							
Injection volume		X		X ⁷										X ⁹		X ⁹							
Concomitant medications/procedures		X ⁶		X	X ⁶	X	X	X	X	X	X	X	X	X ⁶		X ⁶		X		X ⁶		X ¹⁰	
Adverse events		X ⁶		X	X ⁶	X	X	X	X	X	X	X	X	X ⁶		X ⁶		X		X ⁶		X ¹⁰	

This document is confidential.

	Evaluation for repeat-treatment after repeat treatment hold/repeat-treatment ^{4,13}		Follow-up for repeat-treatment ⁵	
	Post repeat-treatment hold Follow-up	Day 3 after Repeat treatment at Visit 7c	4 Weeks Follow up after repeat-treatment at Visit 7c repeat-treatment at Visit 7c	12 Weeks Follow up after repeat-treatment at Visit 7c
	Visit 7c	Phone C, ¹¹	Visit 8c	Visit 9c
Procedure	-	Day 3 after Visit 7c (± 1 day)	Week 4 after Visit 7c (± 5 days)	Week 12 after Visit 7c (± 5 days)
Informed consent				
Medical /aesthetic procedures history ^a				
Demographics ^b				
Fitzpatrick skin type				
Body weight	X		X	X
Visual examinations ^c	X ¹⁰		X ¹⁰	X ¹⁰
Eligibility assessment	X ^{5,6}			
Randomization				
Treatment	X ⁹			
Urine pregnancy test ^d	X ^{5,10}			
NLF-SRS ^e	X ⁶			
Clinical photography ^f	X ⁶			
FACE-Q subject "Satisfaction with Outcome" ^g	X ⁶			
FACE-Q subject appearance "Appraisal of NLFs" ^h	X ⁶			
GAIS' independent blinded evaluating investigator	X ⁶			
GAIS' subject	X ⁶			
Dispense subject diary	X ¹⁰		X ¹⁰	
Collect subject diary ⁱ				
Evaluation of pain ^k	X ¹⁰			
Injection volume	X ⁹			
Concomitant medications/procedures	X ⁶	X	X	X ¹⁰
Adverse events	X ⁶	X	X	X ¹⁰

This document is confidential.

Statistical Analysis Plan for Interventional Studies
Sponsor: Croma-Pharma GmbH; Protocol No.: CPH-301-201200F

- 1 Screening and Baseline visits may be performed as one visit
- 2 Evaluation at Week 2 if a touch-up treatment is needed for optimal correction
- 3 Concerning only subjects who received a touch-up treatment
- 4 Evaluation if a repeat-treatment is needed will be performed at Week 36 (Visit 6) AND/OR at Week 48 (Visit 7) AND/OR Post repeat-treatment hold Follow-up (Visit 7c) according to the criteria presented in [Section 2.6](#) of the protocol
- 5 The first Follow-up visit for repeat-treatment will take place four weeks (± 5 days) after repeat-treatment, i.e. at Week 40 (Visit 8a) for repeat-treatment at Week 36, and at Week 52 (Visit 8b) for repeat-treatment at Week 48. The second Follow-up visit for repeat-treatment will take place twelve (12) weeks (± 5 days) after repeat-treatment, i.e. at Week 48 (Visit 8a) for repeat-treatment at Week 36, and at Week 60 (Visit 8b) for repeat treatment at Week 48.
- 6 Prior to the treatment or any procedure, as applicable
- 7 Touch-up treatment if appropriate for optimal correction
- 8 Only if touch-up treatment occurred at Week 2
- 9 Repeat-treatment at Week 36 (Visit 6) OR Week 48 (Visit 7) OR Post repeat-treatment hold Follow-up (Visit 7c)
- 10 Only if repeat-treatment occurred at Week 36 (Visit 6) OR Week 48 (Visit 7) OR Post repeat-treatment hold Follow-up (Visit 7c)
- 11 All subjects must be asked if they are experiencing or have experienced any signs/symptoms of vision changes or stroke since the injection
- 12 Exclusion criterion based on visual examinations at Baseline
- 13 If a subject was not evaluated for repeat-treatment at Week 36 (Visit 6) and/or Week 48 (Visit 7) due to the hold on repeat-treatment, the subject could attend Visit 7c for evaluation and repeat-treatment (if eligible)
- a Includes information on prior medication, defined as all medication taken/received within the previous ten days
- b Includes date of birth, sex, race and ethnicity
- c Visual examinations (including Snellen visual acuity, confrontational visual fields and ocular motility) to be performed at Baseline and at Week 4; in case of touch-up treatment, to be performed at 4 and 12 weeks after repeat-treatment visit. To be performed prior to- and 30 min after any treatment after all other assessments. The subject should wear the same corrective eyewear (i.e. glasses/contact lenses) at each assessment, if appropriate. The definition of clinically significant changes and action to be taken is presented in Section 10.8.4 of the protocol.
- d In women of childbearing potential only, including those who are postmenopausal for less than twelve months
- e Evaluation and grading of nasolabial folds severity by the treating investigator and by the independent blinded evaluating investigator (separate assessments) will be done using the 5-point NLF-SRS. The Baseline severity is the severity grade assigned at Screening as determined by the treating investigator in conjunction with the independent blinded evaluator. The left and right cheek will be separately evaluated.
- f Clinical photography will be performed; the evaluation and grading of nasolabial folds severity by the independent blinded photographic reviewers using the 5-point NLF-SRS and based on photographs will take place at the end of the clinical investigation. The left and right cheek will be separately evaluated
- g Evaluation of subject satisfaction using the FACE-Q questionnaire "Satisfaction with Outcome"
- h Evaluation of subject appearance appraisal using the FACE-Q questionnaire on "Appraisal of Nasolabial Folds"
- i Evaluation of aesthetic improvement using the Global Aesthetic Improvement Scale (GAIS)
- j Subject diary to be collected and reviewed two and four weeks after initial-touch-up treatment, and four weeks after repeat-treatment
- k Starting 15 min after last injection and at 15 min-intervals for 60 min post-treatment using the adapted NPRS.

This document is confidential.

3. Outcome Measures

The outcome measures will be separately evaluated for the left and right side of the face.

Responder is defined as having at least one grade improvement over Baseline, on the 5-point NLF-SRS.

3.1. Primary Effectiveness Outcome Measures

The percentage of responders based on the independent blinded evaluating investigator live assessment at Week 24 after initial treatment and compared to Juvéderm® Ultra XC. NLF-SRS scores are ranked as 0 (None/minimal), 1 (Mild), 2 (Moderate), 3 (Severe) and 4 (Extreme).

3.2. Secondary Effectiveness Outcome Measures

1. The percentage of responders based on the independent blinded photographic reviewers assessments at Week 24 after initial treatment, compared to Juvéderm® Ultra XC and based on photographs
2. The percentage of responders based on the treating investigator live assessment at Week 24 after initial treatment and compared to Juvéderm® Ultra XC
3. The percentage of subjects with an improvement over Baseline (subjects who have been rated as “very much improved” or “much improved” or “improved”), based on the independent blinded evaluating investigator assessment at Week 24 after initial treatment and using the 5-point GAIS
4. The percentage of subjects with an improvement over Baseline (subjects who have been rated as “very much improved” or “much improved” or “improved”), based on subject assessment at Week 24 after initial treatment and using the 5-point GAIS

3.3. Additional Effectiveness Outcome Measures

1. The percentage of responders based on the independent blinded evaluating investigator live assessment at Week 12, 36, 48 and Visit 7c after initial treatment and compared to Juvéderm® Ultra XC
2. The percentage of responders based on the independent blinded photographic reviewers assessments at Week 12, 36, 48 and Visit 7c after initial treatment, compared to Juvéderm® Ultra XC and based on photographs
3. The percentage of responders based on the treating investigator live assessment at Week 12, 36, 48 and Visit 7c after initial treatment and compared to Juvéderm® Ultra XC
4. The percentage of subjects with an improvement over Baseline (subjects who have been rated as “very much improved” or “much improved” or “improved”), based on the independent blinded evaluating investigator assessment at Week 12, 36, 48 and Visit 7c after initial treatment and using the 5-point GAIS
5. The percentage of subjects with an improvement over Baseline (subjects who have been rated as “very much improved” or “much improved” or “improved”), based on subject assessment at Week 12, 36, 48 and Visit 7c after initial treatment and using the 5-point GAIS
6. The extent of subject satisfaction with outcome of the treatment, as assessed by the Face-Q questionnaire “Satisfaction with Outcome” at Week 12, 24, 36, 48 and Visit 7c after initial treatment
7. Subject appearance appraisal after treatment as assessed by the Face-Q questionnaire “Appraisal of Nasolabial Folds” at Week 12, 24, 36, 48 and Visit 7c after initial treatment, relative to Baseline
8. Subject’s perception of pain after initial with Princess® FILLER Lidocaine and with Juvéderm® Ultra XC and after repeat-treatment with Princess® FILLER Lidocaine, using a scale adapted from the 11-point Numeric Pain Rating Scale (NPRS), where 0 is no pain and 10 is the worst pain imaginable.

This document is confidential.

9. Time from initial to repeat-treatment for each treatment group will be assessed by tabulating the following rates:
 - repeat-treatment at Week 36
 - repeat-treatment at Week 48
 - repeat-treatment at Visit 7c
 - no repeat-treatment
10. Recording of injection volume required to achieve optimal correction for Princess® FILLER Lidocaine and Juvéderm® Ultra XC at initial and touch-up treatments and recording of injection volume required to achieve optimal correction for Princess® FILLER Lidocaine at repeat-treatments (separate assessments)

3.4. Safety Outcome Measures

Frequency, severity, seriousness and causal relationship of AEs, ADEs, SAEs and SADEs during the entire clinical investigation period including subject complaints recorded in the subject diaries during four weeks after initial- and touch-up- treatments, in comparison with Juvéderm® Ultra XC and during four weeks after repeat-treatments, for Princess® FILLER Lidocaine.

This document is confidential.

4. Analysis Sets

4.1. Screened / Randomized Set

The Screened Set will include all subjects who give informed consent and are screened. Unless specified otherwise, this set will be used for summaries of subject disposition.

The Randomized Set will include all subjects randomized. Unless specified otherwise, this set will be used for all subject listings with exception of the listing presenting screening failures and the respective reason(s) for screen failure.

4.2. Full Analysis Set

The Full Analysis Set (FAS) consists of all randomized subjects who received Princess® FILLER Lidocaine AND the control Juvéderm® Ultra XC at the same visit as initial treatment; subjects who receive only one treatment (only Princess® FILLER Lidocaine or only Juvéderm® Ultra XC) during initial treatment will be excluded from the FAS. The analyses based on the FAS will use the randomized treatment groups.

The FAS will be used for effectiveness, demographic, and other baseline characteristics analyses.

4.3. Per-Protocol Set

The Per-Protocol Set (PPS) is defined as a subset of the subjects in the FAS who had no major protocol deviations upto Week 24. Subjects with randomization errors will be considered as major protocol deviations and excluded from PPS.

The PPS will be used for effectiveness analysis.

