9.1 Inclusion and Exclusion Criteria – Screening/Baseline

9.1.1 Inclusion Criteria

Subjects who meet ALL the following criteria are eligible for this clinical investigation:

- 1. Male or female subjects, 22 years of age or older, at the Screening visit
- 2. Subjects with two fully visible, approximately symmetrical moderate to severe NLFs (same severity) with severity scores of 2 or 3 on the 5- point NLF-SRS for both NLF as judged by the treating investigator in conjunction with the independent blinded evaluating investigator.
- 3. Females of childbearing potential must have a negative urine pregnancy test at injection visits and must agree to use an adequate method of contraception for the duration of the clinical investigation
- 4. Healthy skin in the nasolabial area and free of diseases that could interfere in cutaneous aging evaluation
 - 5. Willingness to abstain from any aesthetic or surgical procedures in the treatment area for the duration of the clinical investigation, including botulinum toxin injections (except glabellar or forehead botulinum toxin treatment)
- 6. Subjects having understood the purpose and conduct of the clinical investigation and having given written informed consent

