14.1 Analysis Sets

The statistical analyses will be based on the following data sets:

Full Analysis Set (FAS)

The Full Analysis Set (FAS) consists of all randomized subjects who received at least one administration of Princess[®] FILLER Lidocaine and the control medical device at the same visit; subjects who receive only one treatment (only Princess[®] FILLER Lidocaine or only Juvéderm[®] Ultra XC) during initial treatment will be excluded from the FAS. The analyses based on the FAS will use the randomized treatment groups.

Per-Protocol Analysis Set (PPS)

The Per-Protocol Set (PPS) is defined as a subset of the subjects in the FAS who had no major protocol deviations. A possible per protocol analysis population bias will not be influenced by the exclusion criteria due to the split face design. The excluded subjects due to protocol deviations will be discussed in detail while the statistical analysis plan is being prepared and definitively ahead of the database lock in order to identify any possibly bias.

Safety Analysis Set (SAF)

The Safety Analysis Set (SAF) comprises all subjects who were randomized and received at least one treatment (i.e., any dose of Princess® FILLER Lidocaine or the control medical device). The analyses based on the SAF will use the actual treatment groups.

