The FAS and the PPS will be both considered equally important for the primary analysis. The primary effectiveness analysis will be performed with the FAS; if Princess® FILLER Lidocaine can be considered non-inferior to Juvéderm® Ultra XC according to this analysis, the results of the non-inferiority comparison based on the PPS can be considered confirmatory. Otherwise, the results of this analysis has to be considered exploratory. Overall non-inferiority is demonstrated only if the results are consistent for both analysis data sets. All secondary and additional effectiveness analyses will be conducted for the FAS and PPS.

A hierarchical testing procedure will be applied for the analysis of the primary outcome measure, as well as the key secondary outcome measures, in order to control multiplicity. At this, the following order will be used:

1. Analysis of primary effectiveness based on FAS
2. Analysis of primary effectiveness based on PPS
3. Analysis of key secondary effectiveness # 1 based on FAS
4. Analysis of key secondary effectiveness # 1 based on PPS
5. Analysis of key secondary effectiveness # 2 based on FAS
6. Analysis of key secondary effectiveness # 2 based on PPS

All statistical presentation will be done by treatment group (Princess® FILLER Lidocaine and Juvéderm® Ultra XC). For the primary analysis of the estimands of the primary effectiveness and of key secondary effectiveness endpoints, missing Week 24 assessments of NFL-SRS will be imputed by single imputation as no response. As sensitivity analyses, a best-case analysis (missing values for Princess® FILLER Lidocaine will be considered as a response, missing values for Juvéderm® Ultra XC will be considered as a non-response), a worst-case analysis (missing values for Princess® FILLER Lidocaine will be considered as a non-response, missing values for Juvéderm® Ultra XC will be considered as a response) will be performed on the FAS. Additionally, a tipping point analysis will be conducted on FAS to investigate the robustness of the results, and a complete-case analysis (includes subjects without any missing data) will be performed as supportive analysis.

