Table 14.2.3.1.1	Additional Effectiveness Analysis NLF-SRS Change from Baseline and Response Rate over Time - Blinded Evaluating Investigator	FAS
Table 14.2.3.1.2	Additional Effectiveness Analysis NLF-SRS Change from Baseline and Response Rate over Time - Blinded Evaluating Investigator	PPS
Table 14.2.3.2.1	Additional Effectiveness Analysis NLF-SRS Change from Baseline and Response Rate over Time - Blinded Photographic Reviewer	FAS
Table 14.2.3.2.2	Additional Effectiveness Analysis NLF-SRS Change from Baseline and Response Rate over Time - Blinded Photographic Reviewer	PPS
Table 14.2.3.2.3	Additional Effectiveness Analysis NLF-SRS Over Time Inter-Rater Consistency (Reviewer I vs. II, Reviewer I vs. III, and Reviewer II vs. III) – Blinded Photographic Reviewer	FAS
Table 14.2.3.2.4	Additional Effectiveness Analysis NLF-SRS Over Time Inter-Rater Consistency (Reviewer I vs. II, Reviewer I vs. III, and Reviewer II vs. III) – Blinded Photographic Reviewer	PPS
Table 14.2.3.3.1	Additional Effectiveness Analysis NLF-SRS Change from Baseline and Response Rate over Time - Treating Investigator	FAS
Table 14.2.3.3.2	Additional Effectiveness Analysis NLF-SRS Change from Baseline and Response Rate over Time - Treating Investigator	PPS
Table 14.2.3.4.1	Additional Effectiveness Analysis GAIS Response Rate over Time- Blinded Evaluating Investigator	FAS
Table 14.2.3.4.2	Additional Effectiveness Analysis GAIS Response Rate over Time- Blinded Evaluating Investigator	PPS
Table 14.2.3.5.1	Additional Effectiveness Analysis GAIS Response Rate over	FAS

This document is confidential.

Number	Title	Population
	Time- Subject	
Table 14.2.3.5.2	Additional Effectiveness Analysis GAIS Response Rate over Time- Subject	PPS
Table 14.2.3.6.1	Additional Effectiveness Analysis FACE-Q Subject Satisfaction with Aesthetic Outcome over Time	FAS
Table 14.2.3.6.2	Additional Effectiveness Analysis FACE-Q Subject Satisfaction with Aesthetic Outcome over Time	PPS
Table 14.2.3.7.1	Additional Effectiveness Analysis FACE-Q Subject Appraisal of Nasolabial Folds over Time	FAS
Table 14.2.3.7.2	Additional Effectiveness Analysis FACE-Q Subject Appraisal of Nasolabial Folds over Time	PPS
Table 14.2.3.8.1	Additional Effectiveness Analysis Subjects' Perception of Pain after Initial and Repeat Treatment	FAS
Table 14.2.3.8.2	Additional Effectiveness Analysis Subjects' Perception of Pain after Initial and Repeat Treatment	PPS

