Table 14.2.3.9.1	Additional Effectiveness Analysis Time from Initial to Repeat-Treatment in Days	FAS
Table 14.2.3.9.2	Additional Effectiveness Analysis Time from Initial to Repeat-Treatment in Days	PPS
Table 14.2.3.10.1	Additional Effectiveness Analysis Injection Volume Needed for Optimal Correction in Milliliter (mL)	FAS
Table 14.2.3.10.2	Additional Effectiveness Analysis Injection Volume Needed for Optimal Correction in Milliliter (mL)	PPS
Section 14.3 Safety Data		
Table 14.3.1.1.1.1	Overall Summary of Treatment-Emergent Adverse Events for Initial-treatment	SAF
Table 14.3.1.1.1.2	Overall Summary of Treatment-Emergent Adverse Events for Initial-treatment	SAF
Table 14.3.1.1.2	Overall Summary of Treatment-Emergent Adverse Events for Repeat-Treatment	SAF
Table 14.3.1.2.1	Treatment-Emergent Adverse Events by System Organ Class and Preferred Term for Initial-treatment	SAF
Table 14.3.1.2.2	Study Device Related Treatment-Emergent Adverse Events by System Organ Class and Preferred Term for Initial-treatment	SAF
Table 14.3.1.2.3	Study Procedure Related Treatment-Emergent Adverse Events by System Organ Class and Preferred Term for Initial-treatment	SAF
Table 14.3.1.2.4	Serious Treatment-Emergent Adverse Events by System Organ Class and Preferred Term for Initial-treatment	SAF
Table 14.3.1.2.5	Special Interest Treatment-Emergent Adverse Events by System Organ Class and Preferred Term for Initial-treatment	SAF
Table 14.3.1.2.6	Treatment-Emergent Adverse Device Effects by System Organ Class and Preferred Term for Initial-treatment for Initial-treatment	SAF
Table 14.3.1.2.7	Study Procedure Related Treatment-Emergent Adverse Device Effects by System Organ Class and Preferred Term for Initial-treatment	SAF
Table 14.3.1.2.8	Serious Treatment-Emergent Adverse Device Effects by System Organ Class and Preferred Term for Initial-treatment	SAF
Table 14.3.1.3.1.1	Treatment-Emergent Adverse Events by System Organ Class, Preferred Term, and Maximum Severity for Initial-treatment	SAF
Table 14.3.1.3.1.2	Treatment-Emergent Adverse Events by System Organ	SAF

This document is confidential.

Number	Title	Population
	Class, Preferred Term, and Severity for Initial-treatment	
Table 14.3.1.3.2	Study Device Related Treatment-Emergent Adverse Events by System Organ Class Preferred Term, and Maximum Severity for Initial-treatment	SAF

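### The SAP's per-protocol set ignores major deviations after Week 24, yet it is used for the Week 36, Week 48 and Visit 7c effectiveness tables, and SAP Section 11 does not list the cut

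*SAP*

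**What the plan says.** Protocol 14.1 gives the PPS no time limit: it "is defined as a subset of the subjects in the FAS who had no major protocol deviations". SAP 4.3 narrows this to the "subset of the subjects in the FAS who had no major protocol deviations upto Week 24" and adds: "The PPS will be used for effectiveness analysis". No second PPS is defined for later visits.

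SAP Section 8 applies the set widely: "All secondary and additional effectiveness analyses will be conducted for the FAS and PPS". The table index (SAP Section 15) accordingly has PPS versions, numbered 14.2.3.x.2, of NLF-SRS, GAIS and FACE-Q over time and of injection volume. It also has PPS versions of "Additional Effectiveness Analysis Subjects' Perception of Pain after Initial and Repeat Treatment" and "Additional Effectiveness Analysis Time from Initial to Repeat-Treatment in Days".

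SAP 4.5 says that everyone who meets a Section 4 definition enters the respective analyses. It names eligibility breaches and prohibited concomitant treatments among possible major deviations, and leaves the final decision on populations to the blinded data review meeting. SAP Section 11 lists two changes from the protocol (the estimand approach, and CIs or p-values for lower-ranked objectives); the PPS cut is not one of them.

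Protocol 9.1.1 requires "Willingness to abstain from any aesthetic or surgical procedures in the treatment area for the duration of the clinical investigation", so the commitment runs well past Week 24.

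**The concern.** A per-protocol table at Week 36 or later should show what happens in subjects who have kept to the plan up to that visit. Under SAP 4.3, a subject who has non-study filler in the folds at Week 30 stays in the PPS and can be counted as a responder at Week 36, Week 48 and Visit 7c.

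The FAS does not fill the gap. The SAP's intercurrent-event strategies (Section 5) cover only the Week 24 endpoints. At later visits both sets keep post-Week-24 deviators and differ only through earlier deviations. Agreement between the two sets at Week 48 therefore says nothing about later off-study treatment. What is at stake is the reading of durability for each filler in exploratory tables, and an undeclared departure from the protocol's definition.

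**Working it through.** **Text, side by side.**

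| Question | Source | Answer |
|---|---|---|
| Time limit on PPS in the protocol? | Protocol 14.1 | None |
| Time limit on PPS in the SAP? | SAP 4.3 | Week 24 |
| Is the PPS used after Week 24? | SAP 8; tables 14.2.3.x.2 | Yes, effectiveness |
| Any rule removing later deviators? | SAP 4.3, 4.5 | None written |
| Change declared? | SAP 11 | No |
| Set for repeat-treatment safety? | SAP 4.4, 9, 9.3 | SAF |
| Set for the repeat-treatment subgroup's baseline, history and medication? | SAP 7.2 to 7.4 | FAS (demographics also on the PPS if the sets differ by more than 5%; baseline values precede any late deviation) |
| Status of the later-visit analyses? | Protocol synopsis, General Statistical Considerations | Exploratory |

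**Which deviations matter.** Off-study treatment of the folds reaches the severity and satisfaction ratings. Repeat-treatment in breach of protocol 9.2 mostly does not: NLF-SRS, GAIS, FACE-Q and photographs at Visits 6, 7 and 7c are scheduled before treatment (protocol 2.1, 10.2, 10.7), and the visits after retreatment list no effectiveness ratings (protocol 10.11.12, 10.11.13). Such a breach reaches only repeat-treatment pain, volume and time.

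**Size.** The plan gives no figure for deviations after Week 24, so there is none to reproduce. Let f be the assumed fraction of PPS subjects with both folds corrected off-study and so counted as responders on both sides. The paired difference is (b - c)/n, where b and c are the numbers responding only on the test side and only on the comparator side.

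*Case A: the affected subjects would otherwise be non-responders on both sides.* They move from one concordant cell to the other, so b and c do not change. Each rate rises by f and the difference does not move. With f = 5% of 240 subjects, 12/240 = 5 points on each rate.

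*Case B: the affected subjects are typical of the set, discordant pairs included.* The difference d becomes (1 - f) x d.

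The last two columns show what excluding the affected subjects does in Case A. They use an assumed true late rate of 70%, which becomes 70/(1 - f), and an assumed true difference of -10 points, which becomes -10/(1 - f).

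| f (assumed) | A: rate as planned | B: true d = -10 becomes | A: rate after exclusion | A: true d = -10 after exclusion |
|---|---|---|---|---|
| 2% | 72.0% | -9.8 | 71.4% | -10.2 |
| 5% | 75.0% | -9.5 | 73.7% | -10.5 |
| 10% | 80.0% | -9.0 | 77.8% | -11.1 |

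In counts at 5%: true 168/240 = 70.0%, as planned 180/240 = 75.0%, after exclusion 168/228 = 73.7%. Exclusion recovers 1.3 of the 5 points and scales the difference by 240/228 = 1.053. In Case B exclusion restores d to -10. With f = 0 nothing changes.

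**The case against.** The best case for leaving the plan alone has four parts.

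- **Nothing confirmatory depends on it.** Every affected analysis is exploratory and has an FAS counterpart, and the Week 24 cut is sensible for the Week 24 tests. This stands and sets the priority.
- **Other controls exist.** Protocol 9.3 allows discontinuation for poor compliance or a major violation, so a deviator may never reach Week 36. Protocol 10.9 asks about procedures in the treated area at every contact, and the blinded data review meeting settles the populations. This stands in part: discontinuation is optional, and the written definition gives the meeting no criterion after Week 24.
- **Likelihood is not shown.** No document gives a rate of off-study treatment. Protocol 4.5 cites effects lasting four to twelve months, and some subjects waited through the hold on repeat-treatment, so such treatment is foreseeable, but no more. The 104-week maximum less 12 weeks of follow-up gives Week 92 as a ceiling for repeat-treatment, not an expected wait.
- **Exclusion is informative.** Subjects who seek re-correction because the effect faded are not a random subset. This stands, and Case A shows its size.

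A reader might also infer that all repeat-treatment analyses are compromised, that retreatment outside 9.2 is counted as response, or that correcting both folds always pulls the difference towards zero. The documents do not support the first two, given the safety set and the order of assessments. Case A contradicts the third.

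**Conclusion.** The inconsistency is real and follows from the text alone: a PPS cut at Week 24, no time limit in the protocol, no entry in SAP Section 11, and use of the same set at Week 36, Week 48 and Visit 7c. A subject whose first major deviation is after Week 24 stays in the PPS there. Whether an off-study procedure is major remains for the blinded data review meeting to decide.

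The consequence is possible inflation of each filler's late response rate, by at most the affected fraction, and attenuation of the paired difference only through discordant pairs. Both sizes rest on assumed rates and may be zero. It would be wrong to infer that the non-inferiority conclusion is at risk: the primary and key secondary analyses use Week 24 data, for which the cut is appropriate. Priority: minor, exploratory analyses only.

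**What to change.** 1. In SAP 4.3, keep the Week 24 PPS for the primary, key secondary and other Week 24 endpoints.
2. For effectiveness tables after Week 24, define the PPS by visit: FAS subjects with no major deviation up to the visit analysed, classified at the blinded data review meeting. A breach of 9.2 at a retreatment visit should count for pain, volume and time, but not for ratings taken before the injection. Always show these tables beside the FAS.
3. In SAP Section 11, list the departure from protocol 14.1.
4. Footnote the late PPS tables to say that exclusion after off-study treatment is informative and removes only part of any inflation.

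The cost is SAP wording and one date-based flag built from deviation and concomitant-procedure data already collected. The late PPS tables will have slightly fewer subjects. No clinical procedure changes.
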